8.1.2 Pulse Oximetry

Pulse oximetry will be used to observe oxygen saturation when measuring vital signs. Pulse oximetry will also be used throughout infusions and 2 hours following infusions. Subjects should have a resting oxygen saturation of $\geq 93\%$ in order to be randomly assigned. Subjects requiring oxygen, need the peripheral artery oxygen saturation (SaO_2) to be $\geq 93\%$ when given a maximum of 2L/minute supplemental O_2 via nasal cannula. Infusion toxicity will be assessed based on decreases in oxygen saturation during infusion. The infusion will be stopped if the oxygen saturation does not return to $>93\%$ within 3 minutes of initiating supplemental oxygen or if the subject requires greater than 2L/min supplemental oxygen to achieve the required saturation of $>93\%$. If this occurs then subjects will be admitted to the hospital for observation.

8.1.3 Pregnancy

There is no information regarding allogeneic BMMSCs or UCMSCs and their effects or potential risks to a fetus or unborn child. The Principal Investigator and DSMB must be notified within twenty-four hours of investigator's awareness of the pregnancy via facsimile if a study subject becomes pregnant during the study. Any one of the enumerated contraceptive items will be acceptable for meeting the studies contraceptive requirements as listed in this section. Females will be defined as non-childbearing potential if surgically sterilized (i.e. bilateral tubal ligation, bilateral oophorectomy, or complete hysterectomy) or post-menopausal (defined as 12 months no menses with an alternative medical cause and with a follicle stimulating hormone ($\text{FSH} \geq 25.8 \text{ IU/L}$)). Non-sterilized males who are sexually active with a female partner of childbearing potential must use any one of the enumerated contraceptive items as listed in section 8.2.2 throughout the study.

Acceptable forms of contraception include: 1) abstinence, 2) condoms (male or female) with a spermicidal agent, 3) diaphragm or cervical cap with spermicidal agent, 4) intrauterine device (IUD), 5) oral contraceptive, 6) injectable or transdermal hormonal contraceptive, 7) successful vasectomy with resulting azoospermia or azoospermia for any other reason, and 8) hysterectomy, bilateral oophorectomy, or tubal ligation.

Prior to study enrollment, women of childbearing potential must be advised of the importance of avoiding pregnancy during trial participation and the potential risk factors for a pregnancy. The subject must sign an informed consent and written authorization for use and disclosure of PHI document stating that the above-mentioned risk factors and the consequences were discussed with her.

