4.2 Exclusion Criteria

In order to participate in this study, a subject MUST NOT:

1. Be a female who is pregnant, nursing, or of childbearing potential while not practicing effective contraceptive methods. Female subjects must undergo a blood or urine pregnancy test at screening and within 36 hours prior to infusion.
2. Inability to perform any of the assessments required for endpoint analysis.
3. Active listing (or expected future listing) for transplant of any organ.
4. Clinically important abnormal screening laboratory values, including but not limited to: hemoglobin <8 g/dl, white blood cell count <3000/mm³, platelets <80,000/mm³, INR > 1.5 not due to a reversible cause (i.e. Coumadin), aspartate transaminase, alanine transaminase, or alkaline phosphatase > 3 times upper limit of normal.
5. Serious comorbid illness that, in the opinion of the investigator, may compromise the safety or compliance of the subject or preclude successful completion of the study. Including, but not limited to: HIV, advanced liver or renal failure, class III/IV congestive heart failure, myocardial infarction, unstable angina, or cardiac revascularization within the last six months, or severe obstructive ventilatory defect.
6. Have known allergies to penicillin or streptomycin.
7. Be a solid organ transplant recipient. This does not include prior cell-based therapy (>12 months prior enrollment) bone, skin, ligament, tendon or corneal grafting. Have a history of organ or cell transplant rejection.
8. Have a clinical history of malignancy within 3 years (i.e., subjects with prior malignancy must be disease free for 3 years), except curatively-treated basal cell carcinoma, squamous cell carcinoma, melanoma in situ or cervical carcinoma, if recurrence occurs.
9. Have a non-pulmonary condition that limits lifespan to < 1 year.
10. History of drug abuse (illegal "street" drugs except marijuana, or prescription medications not being used appropriately for a pre-existing medical condition) or alcohol abuse (\geq 5 drinks/day for > 3 months), or documented medical, occupational, or legal problems arising from the use of alcohol or drugs within the past 24 months
11. Be serum positive for HIV, hepatitis BsAg or Viremic hepatitis C, and/or Syphilis – VDRL (If VDRL is reactive Confirmation with FTA-ABS is needed (Syphilis)).
12. Be currently participating (or participated within the previous 30 days) in an investigational therapeutic or device trial.

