7. STUDY PROCEDURES

7.1. Time and Events Schedule

The Time and Events Schedule for the conduct of this study is shown in **Table 11**

Schedule of Assessments
Table 11: Time and Events Table

VISIT	Screening + 45 days	Baseline (0 to -4 weeks prior to Day 0)	Day 0	Week 2 (Day 14) ± 2 days	Month 1 (Day 30) ±1 weeks	Month 3 (Day 90) ±4 weeks	Month 6 (Day 180) ±6 weeks	Month 12 (Day 365) ±2 weeks
Informed Consent	X							
Full Medical History	X							
Physical Exam	X	X	X	X	X	X	X	X
Vital Signs ¹	X	X	X	X	X	X	X	X
12-lead (ECG)	X	X	X	X	X	X	X	X
Concomitant Medications	X	X	X	X	X	X	X	X
Randomization		X						
Infusion Treatment (IP)			X					
6 Minute Walk Test			X			X	X	
4 Meter Gait Speed Test			X			X	X	
QOL Questionnaires (EQ-5D, SF-36, IIEF (Male), SQOL-F(Female))		X			X	X	X	
Laboratory Testing ²								
Review Adverse Events		X	X	X	X	X	X	X
Brachial Ultrasound ³	X	X				X		
Dobutamine Stress Echo (DSE) ⁴	X						X	

Subjects in the pilot phase will receive a telephone call 5 days post infusion (+/- 1 day) to review adverse events

- 1- Weight, Height (will only be collected at screening)
- 2- See table 12 for specific tests done at each time point
- 3- Brachial ultrasound to assess endothelial function should be completed in the morning prior to 12p.m. Instruction for completing this assessment are outline in Appendix 3 of this protocol
- 4- Dobutamine Stress Echocardiogram (DSE) will be performed, at screening and at the Month 6 follow-up visit. Instructions for completing the (DSE) are outlined in Appendix 2 of this protocol. If the stress test needs to be stopped due to unforeseeable side effects and cannot be completed on a subject, this will not prevent them from being able to take part in the study.

Schedule of Laboratory Testing
Table 12: Time and Events Table

VISIT		SCR	BSL	DAY 0	W2	M 1	M 3	M 6	M 12
Standard Labs	CBC with Differential ¹	X		X	X	X	X	X	
	Comprehensive Metabolic Panel ²	X		X	X	X	X	X	
	PT, INR, PTT	X							
	Uric Acid, Pro BNP, hsCRP, IL6, Fib, D-dimer, TNFa,	X		X	X	X	X	X	
	Lipid Profile ³	X		X	X	X	X	X	
	Urinalysis	X		X		X	X	X	
	HbA1c	X				X	X	X	
	Pregnancy (childbearing women) ⁴	X		X					
Biomarkers / Immune	SST / PRA ⁵			X				X	
	MNCs ⁶			X	X	X	X	X	
EPCs	Endothelial Blood Samples ⁷		X				X		
Gene Expression	DNA ⁸			X					
	RNA			X				X	
Viral Serology	Infectious Disease Tests ⁹	X							

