8.1.1 Laboratory Evaluations

At screening, the HIV-1 and HIV-2 tests, Syphilis – VDRL (If VDRL is reactive Confirmation with FTA-ABS is needed), CMV, hepatitis screen and β -HCG serum pregnancy tests (only for women of childbearing potential) will be performed locally at the study site. Laboratory safety tests will consist of the following:

Serum chemistry: sodium, potassium, chloride, BUN, creatinine, glucose, calcium, AST/SGOT, ALT/SGPT, carbon dioxide, total bilirubin (fractionate if total >1.5 times normal), alkaline phosphatase, albumin, fibrinogen, IL6, D-Dimer, Coagulation studies

Hematology: hemoglobin, hematocrit, platelets, WBC, RBC,

The Investigator will review all clinically relevant laboratory results requested in the protocol. The diagnosis associated with any clinically significant laboratory deviations should be recorded as an AE and should indicate the underlying abnormality or diagnosis (such as renal insufficiency) as opposed to the observed deviation in laboratory results (such as elevated creatinine). If there is no underlying abnormality linked to a clinically significant abnormal laboratory value, the observed deviation should be reported as the AE.

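### The definition of post-menopausal in section 8.1.3 contradicts the term it defines, and the FSH and pregnancy-test provisions that depend on it do not agree with one another

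*Combined protocol and SAP*

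**What the plan says.** The only definition of childbearing potential is in section 8.1.3. It opens "Females will be defined as non-childbearing potential if surgically sterilized" and gives post-menopausal status as the other route. That status is "post-menopausal (defined as 12 months no menses with an alternative medical cause" "and with a follicle stimulating hormone" of 25.8 IU/L or more, so both conditions must be met.

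Four provisions depend on this classification:

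- Exclusion 1 (synopsis and section 4.2) bars a woman who is "of childbearing potential while not practicing effective contraceptive methods".
- Section 8.1.3 requires that "women of childbearing potential must be advised of the importance of avoiding pregnancy during trial participation".
- Section 8.1.1 lists screening "serum pregnancy tests (only for women of childbearing potential").
- Table 12 in section 7.1 has the row "Pregnancy (childbearing women"), marked at screening and Day 0.

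Exclusion 1 also contains a testing sentence that requires a blood or urine test of female subjects at screening and within 36 hours before infusion. That sentence has no childbearing-potential limit.

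**The concern.** In a definition of menopause, an alternative medical cause can only be a cause other than menopause. The text therefore makes a condition of the very finding that would argue against menopausal status. The wording is operative, because it decides who must use contraception, who is counselled and, under two of the passages, who is pregnancy-tested. Enrolment is open from age 21, so women of reproductive age can enter, and section 8.1.3 itself states that nothing is known about fetal risk from these cells. A rule protecting against fetal exposure should not depend on each site deciding how to read a contradictory sentence.

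**Working it through.** No arithmetic applies and the plan has no figure to reproduce. The check was to apply the definition literally to a woman who is not surgically sterilized and reports 12 months without menses, and then to follow the result into each dependent rule.

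**Step 1: classification.** The inputs are the two conditions in section 8.1.3, joined by "and".

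| Alternative medical cause? | FSH | Class under the literal text |
|---|---|---|
| Yes | 25.8 IU/L or more | Non-childbearing |
| Yes | Below 25.8 IU/L | Childbearing potential |
| Yes | No value | Childbearing potential |
| No | 25.8 IU/L or more | Childbearing potential |
| No | Below 25.8 IU/L | Childbearing potential |
| No | No value | Childbearing potential |

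Only the first of the six rows leaves the safeguards, and it is a row in which the amenorrhoea has another explanation. The three rows with no alternative cause all stay in the childbearing class whatever the FSH.

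**Step 2: consequences for the woman in the first row.**

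- Contraception: exclusion 1 does not reach her on this ground, and no other passage imposes the requirement on her.
- Counselling: the duty in section 8.1.3 is limited to women of childbearing potential, so it does not cover her.
- Pregnancy test: Table 12 and section 8.1.1 leave her out. The testing sentence of exclusion 1, read as written, includes her. The passages conflict, and the answer depends on which one the site follows.

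**Step 3: consequences for a woman with no alternative cause.** She is handled as of childbearing potential, with contraception, counselling and tests. She need not be excluded, because exclusion 1 bars only women who do not practise contraception and the list in section 8.1.3 accepts abstinence.

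**Step 4: is FSH available?** FSH does not appear in Table 12, in its footnotes or in the laboratory list of section 8.1.1. A site that follows the schedule has no value, and by the table in step 1 that puts the woman in the childbearing class. The definition thus relies on a measurement that the schedule does not provide, but the default is protective.

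**Step 5: cross-reference.** Section 8.1.3 sends men to a contraceptive list in section 8.2.2. Section 8.2 defines adverse events and has no such subsection; the list is in section 8.1.3 itself. This is clerical.

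**The case against.** The strongest reply is that the definition cannot do much harm. Because the conditions are joined by "and", a fertile woman leaves the safeguards only if an FSH is obtained and reaches the threshold. If the missing FSH test is taken at face value, nobody qualifies as post-menopausal and every woman who is not sterilized stays protected. The opposite error costs a woman a test and a contraception requirement. Exclusion 1 still tests all female subjects before the single infusion and bars any who are pregnant. An experienced investigator may also see the qualifier as a drafting slip.

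Most of this stands. A reader might infer that no woman with amenorrhoea can be classified correctly, or that the missing FSH test removes the last safeguard. The documents do not support either reading. A woman with another cause and an FSH that is low or absent is kept in the childbearing class, and a missing FSH keeps women inside the safeguards. The absence of FSH from the schedule also does not stop a site from obtaining it or using a documented result.

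That last point works in both directions: once a value is obtained, the first row of the table can occur. The contraception and counselling requirements then have no backstop elsewhere. The pregnancy-test backstop is contradicted by two other passages. A rule that is safe only if staff silently reinterpret it should still be corrected.

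**Conclusion.** The definition is internally contradictory and is the only one in the protocol. The safety-relevant error is confined to women who are not surgically sterilized, whose 12 months of amenorrhoea have another medical cause, and whose FSH is 25.8 IU/L or more. They fall outside contraception and counselling, and outside pregnancy testing if Table 12 and section 8.1.1 prevail over exclusion 1. The error in the other direction is an unnecessary burden. The size of the exposed subgroup cannot be derived from the documents. The conclusion assumes that sites apply the text literally and that an FSH value is available for the women concerned. Sample size, significance level and the planned analyses are not affected.

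**What to change.** In one amendment, the sponsor should:

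- reconcile the amenorrhoea qualifier in section 8.1.3 with the term it defines;
- reconcile the FSH condition with Table 12, its footnotes and section 8.1.1, so that the definition and the laboratory schedule agree;
- make exclusion 1 (synopsis and section 4.2), Table 12 and section 8.1.1 agree on which women are pregnancy-tested;
- correct the reference to section 8.2.2.

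Which clinical rule to adopt is for the sponsor to decide. The cost is a text and schedule amendment, with at most one added assay on the existing screening draw for a subset of women.

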8.1.4 Determination of Infusional Toxicity

Infusional toxicity will be evaluated by continuously monitoring the subject's vital signs and O_2 saturation by pulse oximetry from the time of allogeneic BMMSCs or UCMSCs

administration until two hours after infusion is complete. Since there is no specific or antidotal therapy for AEs arising from allogeneic BMMSCs or UCMSCs, any toxicity that may arise during a subject's participation in this study should be managed with supportive measures at the discretion of the treating physician.

8.1.5 Subject Stopping Guidelines

This guideline is to be used to indicate boundaries requiring discussion by the Data and Safety Monitoring Board (DSMB) and is designed to assist the independent DSMB in overseeing the study. The DSMB may also request additional interim analyses and develop other criteria including provision for monitoring of potential late effects to determine when to intervene in the enrollment or treatment of subjects in the study. The first more conservative stopping guideline is to monitor subjects for unexpected SAEs where there is a reasonable possibility that the study product or administration procedure caused the event within 30 days of administration including subject death, grade 3 myocardial infarction, grade 3 hemodynamically unstable ventricular tachycardia or grade 3 LV perforation. Study accrual and further treatment of subjects will be put on hold if any subjects experience one of these events. The DSMB will be notified within 24 hours of the occurrence of these events and will be convened within 3 business days to review the event and study.

The following are subject stopping guidelines:

5. Any subject who develops persistent (that is, still existing more than 3 hours after the end of IP infusion) cardiorespiratory signs or symptoms (for example, shortness of breath, tachypnea, tachycardia, Bradycardia, hypotension, or palpitations) will continue with all scheduled follow-up if such follow-up is considered safe in the opinion of the Investigator.
6. Any subject whose infusion is stopped due to cardiorespiratory distress will receive no further IP infusions but will continue with all scheduled follow-up if such follow-up is considered safe in the opinion of the Investigator.
7. Any subject who develops any sign or symptom that, at the discretion of the Investigator, warrants the discontinuation of infusion will receive no further IP infusions but will continue with all scheduled follow-up if such follow-up is considered safe in the opinion of the Investigator.
8. Infusion of the IP may be stopped if there is an adverse event that the Investigator believes is related to the IP or if there is an issue with the IP infusion.
9. The proportion of subjects experiencing TE-SAE as defined in Section 2.2.1 will be monitored within 30 days of infusion. This guideline is designed to assist the independent DSMB in overseeing the study and indicate boundaries needing discussion by the DSMB. The DSMB may also request additional interim analyses

and develop other criteria including provision for monitoring of potential late effects to determine when to intervene in the enrollment or treatment of subjects in the study.

10. Monitoring of key safety endpoints (refer to Table 8 in section 2.2.1) will be conducted.
11. The stopping guidelines serve as a mechanism for consultation with the DSMB for additional review, and are not formal “stopping rules” that would mandate automatic closure of study enrollment. It is designed to assist the independent DSMB in overseeing the study. The DSMB may also request additional interim analyses and develop other criteria including provision for monitoring of potential late effects to determine when to intervene in the enrollment or treatment of subjects in the study.
12. Study accrual and further treatment of subjects will be stopped if multiple (i.e. more than 1) subjects develop cardiorespiratory signs and symptoms that are persistent or lead to discontinuation of infusion.

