2.2 Study Endpoints

2.2.1 Primary Endpoints (Safety)

Safety will be assessed as the incidence within one month after an infusion of any treatment emergent serious adverse events (TE-SAEs), defined as one or more of the following events that: is life-threatening event (e.g., stroke or non-fatal pulmonary embolism); requires inpatient hospitalization or prolongation of existing hospitalization (e.g., for worsening dyspnea); results in persistent or significant disability/incapacity; results in death; or leads to clinically significant untoward laboratory test result(s) or medical condition(s), determined per Investigator' judgments.

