3. STUDY DESIGN

3.1 Description of the Study

A Pilot Phase will be performed to test the safety of dose and volume of cells administered via peripheral intravenous infusion. The first three (3) subjects in-group 1 (UCMSCs) will be treated first and safety will be fully assessed. Only if there is no evidence of treatment emergent SAEs in Group 1, treatment of subjects in Group 3 be undertaken.

The subjects in the high dose (Groups 3 & 4) will not be treated until the subjects in the low dose (Groups 1 & 2) have completed their one-month follow-up assessments and safety measures have been reviewed to confirm that there have been no treatment emergent SAE's. Treatment emergent SAE's, defined as the composite of: death, non-fatal pulmonary embolism, stroke, hospitalization for worsening dyspnea and clinically significant laboratory test abnormalities, prior to proceeding with the treatment of further subjects.

Subjects in each pilot phase group (Group 1, 2, 3 and 4) will not be treated less than 5 days apart.

Subjects in the pilot phase will receive a telephone call 5 days post infusion (+/- 1 day) to review adverse events.

The randomized portion of the study will be conducted after a full review of the safety data from the Pilot Phase by the DSMB.

Following the pilot study (12 subjects), thirty (30) subjects that meet inclusion criteria will be scheduled to undergo peripheral intravenous infusion.

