9.4.3.3 Data Review Meetings

After all patients enrolled in the Pilot Phase have received the study therapy infusion and been followed for 30 days, the DSMB will conduct a full review of all cumulative safety data before the trial proceeds to the Randomized Phase. As part of the cumulative safety data review meeting for the pilot phase, the DSMB will recommend that the trial proceed to the protocol-specified randomized phase or recommend a dose modification for the randomized placebo study.

Ongoing Monitoring During Randomized Phase

Formal data review meetings that include the entire DSMB will be conducted via teleconference approximately every three months. The timeline for the quarterly DSMB data review meetings will begin after approximately 25% of patients are enrolled in the randomized phase. Meetings may be postponed due to accrual rates at the DSMB's discretion. The purpose of the data review is for safety evaluation, and the study may be stopped because of significant safety concerns. SAEs which are related to stopping rules will be continuously evaluated and the full DSMB will be informed of any extra risk. The DSMB will evaluate all safety data available for each patient as appropriate.

Open session

Blinded data will be provided to the DSMB approximately 1 week before each data review meeting. The report will contain:

1. Protocol status including any protocol changes
2. Data sources and cutoff dates
3. Analysis methods applied specifically to the open session report
4. Subject enrollment by month
5. Protocol deviations
6. Early treatment discontinuations and study withdrawals
7. Demographic and baseline characteristics
8. Duration of follow-up at time of data cutoff

Closed Session

Only the DSMB members will participate in closed sessions. Unblinded data will be presented to the DSMB in closed session and discussed by the DSMB. "Unblinded" means that the name of actual treatment arm is associated with individual subject data listings and summaries of data. At the chairperson's discretion, the DSMB may discuss or vote on potential study conduct recommendations at closed session.

The closed session report will contain data separated and identified by treatment group. This report (hard copy) will be provided to the DSMB approximately 1 week before each data review meeting and will include:

1. Data sources and cutoff dates
2. Analysis methods applied specifically to the closed session report
3. Subject enrollment
4. Protocol deviations

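### The one-event dosing hold in 8.1.5 does not fit an intravenous trial, and its wording leaves unclear whether a related non-fatal embolism or stroke triggers it

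*Combined protocol and SAP*

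**What the plan says.** The combined protocol and SAP, section 8.1.5, describes its first and more conservative guideline. It concerns unexpected SAEs that the product or the procedure may reasonably have caused, "within 30 days of administration including subject death, grade 3 myocardial infarction, grade 3 hemodynamically unstable ventricular tachycardia or grade 3 LV perforation". The consequence follows: "Study accrual and further treatment of subjects will be put on hold if any subjects experience one of these events". The reporting clock refers back in the same way: "The DSMB will be notified within 24 hours of the occurrence of these events and will be convened within 3 business days".

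Four other places bear on this list:

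- Section 2.2.1 (primary safety endpoint) counts, among other criteria, an event that "is life-threatening event (e.g., stroke or non-fatal pulmonary embolism); requires inpatient hospitalization or prolongation of existing hospitalization (e.g., for worsening dyspnea".
- Section 3.1 (gate from low to high dose) describes treatment-emergent SAEs as "defined as the composite of: death, non-fatal pulmonary embolism, stroke, hospitalization for worsening dyspnea and clinically significant laboratory test abnormalities".
- Section 8.9 rates intensity as mild, moderate, severe or life-threatening. It has no numbered grades.
- Section 8.14 has every AE documented as unexpected.

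**The concern.** All dosing is by peripheral intravenous infusion, and section 1.3 reports that cells given this way go mainly to the lung. One would expect the single-event hold to name pulmonary and thromboembolic events. It names a perforated ventricle instead, which is not a plausible result of infusion into a peripheral vein.

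The scope is also uncertain. If the four items are only examples, a possibly related non-fatal embolism or stroke stops dosing at once and brings the DSMB together within 3 business days. If the four items are the whole trigger, the same event does neither. The Synopsis describes the study as a safety assessment ahead of a full comparator trial, so that difference should not be left to the reader.

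**Working it through.** The plan states no boundary or error rate for this hold, so there is no figure to reproduce. The check is textual, with two short calculations under assumed or worst-case inputs.

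**1. Named events compared.**

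| Event | Hold list, 8.1.5 | Example in 2.2.1 | Component in 3.1 |
|---|---|---|---|
| Death | named | criterion, not an example | yes |
| Non-fatal pulmonary embolism | not named | yes | yes |
| Stroke | not named | yes | yes |
| Admission for worsening dyspnoea | not named | yes | yes |
| Significant laboratory abnormality | not named | criterion, not an example | yes |
| MI, unstable VT, LV perforation | named (grade 3) | no | no |

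The hold names 0 of the 3 examples in 2.2.1 and 1 of the 5 components in 3.1 (death). This counts names only. Section 2.2.1 works by seriousness criteria, so an MI or unstable VT that is life-threatening or needs admission also counts there.

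**2. The two readings.** For the broad one: the class of related SAEs is defined before the list, 'including' introduces examples, and 8.14 removes 'unexpected' as a filter. For the narrow one: the hold sentence speaks of one of these events directly after four items, and limiting MI and VT to grade 3 does no work if every related SAE already triggers the hold. No other text in the documents decides between them.

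**3. What depends on the reading.** The automatic hold, and the 24-hour notice with the 3-business-day meeting.

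**4. Whether other provisions close the gap.**

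| Provision | What it gives | Pauses dosing within a stage after one event? | Sets a meeting deadline after an event? |
|---|---|---|---|
| 8.1.5 item 9 | Monitors the TE-SAE proportion to 30 days | No | No |
| 8.1.5 item 12 | Stops after more than 1 subject with cardiorespiratory signs that persist or end the infusion | No | No |
| 8.12 | SAE recorded in 48 hours, or 24 if fatal or life-threatening | No | No |
| 9.3 | Chair told of each SAE | No | No |
| 9.4.3.2 | Monthly safety reports, optional teleconference | No | No |
| 9.4.4.3 | Extra analyses, unscheduled meeting | At DSMB discretion | No |
| 3.1 and 9.4.3.3 | Low-dose gate; review after the pilot | Between stages only | No |

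**5. Item 12 as a substitute (assumed rates).** Cells go to 12 + 20 = 32 subjects. Suppose each has a risk p of a related embolism or stroke, with p from 1% to 5% (an assumption). P(at least 1) = 1 − (1 − p)^32, which is 0.275 to 0.806. P(at least 2) = 1 − (1 − p)^32 − 32p(1 − p)^31, which is 0.041 to 0.480. So even if every such event met item 12, its two-subject threshold would be reached much less often than a one-event trigger.

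**6. Worst-case exposure on the narrow reading.** This also assumes that neither the investigator nor the DSMB acts.

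- Event in the first high-dose pilot subject: 6 − 1 = 5 more high-dose subjects before the post-pilot review, 3 − 1 = 2 of them on the same product. The spacing rule is "Subjects in each pilot phase group (Group 1, 2, 3 and 4) will not be treated less than 5 days apart".
- Event in the first randomised subject: "The timeline for the quarterly DSMB data review meetings will begin after approximately 25% of patients are enrolled in the randomized phase". 0.25 × 30 = 7.5, about 8, so about 8 − 1 = 7 further enrolments before that timeline begins. About a third of randomised subjects (10 of 30) receive placebo.

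**The case against.** The strongest reply is that the ordinary reading already gives the right answer. 'Including' normally introduces examples, the paragraph calls itself the more conservative guideline, and 8.14 lets no event escape as expected. LV perforation is then surplus and cannot weaken the hold. This largely stands. A reader might infer that a related embolism or stroke is excluded from the hold, and the documents do not support that. They show only that the wording does not settle the question. A fatal related event triggers the hold on either reading.

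A reader might also infer that closer surveillance is lost on the narrow reading, because 9.4.3.3 says "SAEs which are related to stopping rules will be continuously evaluated and the full DSMB will be informed of any extra risk". That does not follow. Item 9 sits among the same guidelines and monitors TE-SAEs as 2.2.1 defines them, so embolism and stroke are plausibly covered either way.

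Nor do the documents support expecting dosing to run on for months. The Chair hears of every SAE, safety reports are monthly, SAEs are recorded within 24 or 48 hours, and pilot subjects are telephoned about day 5. These bring information and allow discretion. What remains is that none of them imposes a pause or a date.

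Finally, 9.3 places DSMB policies in a Charter, and item 10 refers to a Table 8. Neither is in the documents, and either might settle the matter or hold a TE-SAE boundary.

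**Conclusion.** The point holds as a modest, safety-relevant defect of wording. On either reading the list is poorly matched to the route (LV perforation), to the protocol's own intensity scale ('grade 3') and to its own key safety events (0 of 3 named). On scope, the broad reading is the likelier one, but the text permits the narrow one. For a possibly related non-fatal embolism or stroke, the difference is an automatic hold with a DSMB meeting within 3 business days, against no automatic hold and no deadline. It matters only within a stage: within a pilot dose level or during the randomised phase.

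The counts of 5 and about 7 further subjects are worst cases that need the narrow reading, an event in the first subject of the stage and no action by anyone. They are not expected exposures. The conclusion assumes that neither the Charter nor Table 8 already resolves the scope.

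**What to change.** Rewrite the hold paragraph along these lines: enrolment and dosing pause when any subject has, within 30 days of infusion, an SAE that the product or the procedure may reasonably have caused. Examples are death, any life-threatening event, pulmonary embolism, stroke, hospitalisation for worsening dyspnoea, and severe or life-threatening MI or unstable VT. Delete LV perforation, replace 'grade 3' with the 8.9 categories, and attach the 24-hour notice and the 3-business-day meeting to this same defined event. The relatedness condition stays. Omitting 'unexpected' changes nothing while 8.14 stands. If the Charter holds a TE-SAE boundary, cross-refer to it in item 9.

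The cost is one amended paragraph, with no new data, visits or committee. The downside is an occasional short pause for an event later judged unrelated. If an assumed 1% to 5% of the 42 subjects had a possibly related SAE outside the present list, that is 42 × 0.01 = 0.42 to 42 × 0.05 = 2.1 extra pauses over the whole trial compared with the narrow reading. If the broad reading is already intended, there are none.
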